6.7. Intervention After the End of the Study

This is a healthy participant study and no follow-up intervention is planned.

7. DISCONTINUATION OF STUDY INTERVENTION AND PARTICIPANT DISCONTINUATION/WITHDRAWAL

7.1. Discontinuation of Study Intervention

In rare instances, it may be necessary for a participant to permanently discontinue (definitive discontinuation) the study intervention. If the study intervention is definitively discontinued, the participant should remain in the study to be evaluated for safety follow-up. See the SoA for data to be collected at the time of discontinuation of study intervention and follow-up and for any further evaluations that need to be completed.

Participants should be considered for discontinuation from intervention if any of the following occur during the study:

- Serious hypersensitivity reaction;
- Severe uncontrolled infection;
- Use of disallowed medication as defined in Section 6.5;
- Pregnancy or planned pregnancy; or
- Alexion or the Investigator deems it is necessary for the participant.

See the SoA for data to be collected at the time of intervention discontinuation and follow-up and for any further evaluations that need to be completed.

7.2. Stopping Criteria

7.2.1. Individual Stopping Rules

Study drug administration to an individual participant will be continued, delayed, temporarily suspended, or discontinued immediately (if applicable) and permanently if AEs related to the study drug occur as detailed in [Table 20](#):

Table 20: Individual Stopping Rules

Adverse Events Related to ALXN1820	Action ^a
Moderate (CTCAE Grade II except for injection site reactions, QT interval prolongation, hematology, and liver function, which are specified below)	Study drug administration may be continued, delayed, temporarily suspended, or discontinued in accordance with Investigator's clinical judgment, in consultation with the Sponsor
Injection site reactions: Moderate (CTCAE Grade II)	Study drug administration will be discontinued if not reduced at least to Grade 1 by the time of next dose
QT interval prolongation: A prolongation of the uncorrected QT interval of greater than 500 ms, using consistent, technically valid triplicate ECG	Study drug administration will be discontinued
Hematology: Hb drop to absolute values of < 10 g/dL (100 g/L) Platelet count drop to absolute values of < 75,000/mm ³	
Severe (CTCAE Grade III)	
CTCAE Grade IV Or Serious Or Hy's law: ALT or AST value > 3 × ULN together with bilirubin increase > 2 × ULN, without other evidence of cholestasis Or ALT or AST value > 8 × ULN ALT or AST value > 3 × ULN, and symptomatic	

^a Actions are only relevant for multiple dosing regimens where additional doses are planned for administration. Abbreviations: ALT = alanine aminotransferase; AST = aspartate aminotransferase; CTCAE = Common Terminology Criteria for Adverse Events; ECG = electrocardiogram; Hb = hemoglobin; IV = intravenous; ULN = upper limit of normal.

7.2.2. Cohort and Study Safety Stopping Rules

A cohort and other cohort with a dose at an equal or higher level will be stopped or not initiated if any of the following occurs ([Table 21](#)):

Table 21: Cohort and Study Stopping Rules

Adverse Events Related to ALXN1820	Showing Signs of Reversibility	Number of Participants	Action
Moderate (CTCAE Grade II except for injection site reactions, QT interval prolongation, hematology, and liver function, which are specified below)	Yes	≥ 3 in 1 SOC ≥ 4 total in different SOCs	Cohort: Dosing of the remainder of the cohort suspended Study: Dosing of equal or higher doses suspended
	No	≥ 2 total in different SOCs	
Injection site reactions: Moderate (CTCAE Grade II)	No ^a	≥ 3	Dosing of lower dose levels can continue Continuation of dosing of equal or higher doses requires a substantial amendment ^b
QT interval prolongation: A prolongation of the uncorrected QT interval of greater than 500 msec, using consistent, technically valid triplicate ECG	NA	≥ 2	
Hematology: Hemoglobin drop to absolute values of < 10g/dL (100 g/L). Platelet count drop to absolute values of < 75,000/mm ³	NA	≥ 2	
Severe (CTCAE Grade III)	NA	2	Study suspended (all dosing [lower, equal or higher doses] suspended)
CTCAE Grade IV Or Serious Or Hy's law: ALT or AST value > 3 × ULN together with bilirubin increase > 2 × ULN, without other evidence of cholestasis Or ALT or AST value > 8 × ULN ALT or AST value > 3 × ULN, and symptomatic	NA	1	Continuation of the cohort or study requires a substantial amendment ^b

^a For injection-site reactions, a cohort and/or the study will be suspended when ≥ 3 participants are observed. If all but 1 affected participant show signs of recovery (at least to Grade 1), cohort and study continuation can then proceed. If ≥ 2 participants remain at Grade 2 after the minimum data review period, the period of observation should be extended for up to 168 hours. If all but 1 affected participant show sign of recovery (at least to Grade 1), cohort and study continuation can then proceed. If ≥ 2 affected participants remain at Grade 2 after the first 168-hour extension period, the SRC will make the decision to either prolong further the observation period up to a maximum of another 168 hours, or suspend the remainder of the cohort and study. At the end of the second extension period, if all but 1 participant show sign of recovery (at least to Grade 1), cohort and study continuation can then proceed. If, however, ≥ 2 affected participants remain at Grade 2, cohort and study will be suspended.

^b A substantial amendment may include an amendment to the protocol, the ICF, or other study-related documents as appropriate.

Abbreviations: ALT = alanine aminotransferase; AST = aspartate aminotransferase; CTCAE = Common Terminology Criteria for Adverse Events; ECG = electrocardiogram; Hb = hemoglobin; ICF = informed consent form; IV = intravenous; NA = not applicable; SOC = System Organ Class; SRC = Safety Review Committee; ULN = upper limit of normal.

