6.6. Dose Modification

Decisions to continue or modify dosing will be made by the Investigator and/or SRC after review of the blinded data as described in [Table 19](#). The SRC may also make recommendations regarding safety issues, study conduct, or study suspension.

Table 19: Study ALXN1820-HV-101 Dose Continuation/Escalation Decision Pathway

Dosing Decision	Responsible Party	Data to be Reviewed	Documentation/Communication Methods
Continuation from the sentinel participant to the remaining participants	Investigator	A minimum of 48 hours post-dose safety and tolerability data from the sentinel participant.	The Investigator will document the decision in an email to the Sponsor. The email does not require the Sponsor's response, unless there is disagreement with the Investigator's decision.
Dose escalation from Cohort 1 to 2, Cohort 2 to 3, Cohorts 3 to 4	SRC	All available data up to a minimum of 336 hours post-dose safety and tolerability data from at least 7 participants (of whom at least 5 will have received treatment) from the previous cohort.	The SRC will document the decision on the escalation/progression approval form.
Proceed to Cohort 5	Investigator or SRC	A minimum of 168 hours post-dose safety and tolerability data from at least 7 participants (of whom at least 5 will have received treatment) from Cohort 4.	The Investigator will document the decision in an email to the Sponsor. The email does not require the Sponsor's response, unless there is disagreement with the Investigator's decision. In case there are safety findings in previous cohorts, an SRC review will be conducted and dosing for Cohort 5 may be started at the planned dose of 450 mg IV or a lower dose.
Escalation to Cohort 6	SRC	All available data up to a minimum of 336 hours post-dose safety and tolerability data from at least 7 participants (of whom at least 5 will have received treatment) from each of cohorts 4 and 5.	The SRC will document the decision on the escalation/progression approval form.

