9.5. Safety Review Committee (SRC)

An SRC, consisting of Investigators from participating sites, Safety physician, Medical Monitor, Study Statistician, and Clinical Pharmacologist, will evaluate the study data at prespecified time points for participant safety and make recommendations on dose escalation, dose modification, or termination of the study. In the event a significant safety issue is identified, an ad hoc SRC meeting will be convened within 24 hours following its identification (see SRC charter for description of membership, schedule of meetings, data required for each safety review, and requirements for documenting meeting discussions and outcome).

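### Table 21 sets no one-SOC count for non-reversible Grade II events: read literally, 3 to 6 of them in one SOC trigger nothing, while 3 reversible ones suspend dosing

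*Protocol*

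**What the plan says.** Protocol 7.2.2 makes the rule mandatory: the cohort, and any other at an equal or higher dose, "will be stopped or not initiated if any of the following occurs". The rows at issue cover related events classed as "Moderate (CTCAE Grade II except for injection site reactions, QT interval prolongation, hematology, and liver function, which are specified below". They are split by whether the event shows signs of reversibility:

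- **Reversible:** "≥ 3 in 1 SOC ≥ 4 total in different SOCs"
- **Not reversible:** "≥ 2 total in different SOCs"

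Meeting either row suspends dosing of the rest of the cohort and of equal or higher doses. Resuming those doses needs a substantial amendment.

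Other text that bears on persistent Grade II events:

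- **Table 21, footnote a** covers injection-site reactions only. After at least 3 such reactions and the permitted extensions of observation, it ends: "If, however, ≥ 2 affected participants remain at Grade 2, cohort and study will be suspended".
- **Table 20 (Protocol 7.2.1)** leaves the same class of Grade II event to the Investigator's judgment, in consultation with the Sponsor: "Study drug administration may be continued, delayed, temporarily suspended, or discontinued". Its footnote limits these actions to multiple-dose regimens.
- **Protocol 6.6:** "The SRC may also make recommendations regarding safety issues, study conduct, or study suspension".
- **Protocol 9.5:** if a significant safety issue is identified, "an ad hoc SRC meeting will be convened within 24 hours following its identification".

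The SAP does not restate the stopping rules.

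**The concern.** A persistent event should stop dosing at least as readily as a resolving one. Across different SOCs Table 21 does this, with 2 participants for non-reversible events against 4 for reversible. Within one SOC the literal text does the reverse: reversible events have a count of 3 and non-reversible events have none.

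Clustering in one organ class is a pattern one would expect a stopping rule to catch. This is a first-in-human study of a drug with an expected half-life of about 24 days at the highest SC dose (Protocol 4.2) and no antidote (Protocol 6.3 and 8.4). Under Protocol 4.1, dosing the rest of a cohort depends on no Section 7.2 criterion having been met, and under Table 19 the Investigator alone decides whether to go beyond the sentinel pair. The table is therefore a working gate between SRC meetings. If its wording allows two readings, two people could act differently on the same data.

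**Working it through.** Table 21 gives rule counts, so there is no sample size or power figure to reproduce. The check applies both rows literally, then prices the repair.

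**Inputs from the documents.** The two Grade II cells of Table 21, and 6 active plus 2 placebo participants per cohort (Table 14).

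**Rules as written**, with one event per participant:

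- Reversible row fires if the largest count in any one SOC is ≥ 3, or if the total is ≥ 4 over at least two SOCs.
- Non-reversible row fires if the total is ≥ 2 over at least two SOCs.

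**Results:**

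| Pattern | Reversible row | Non-reversible row |
|---|---|---|
| 2 in one SOC | no | no |
| 3, 4, 5 or 6 in one SOC | suspends | **no** |
| 2 or 3, each in a different SOC | no | suspends |
| 4 or more, each in a different SOC | suspends | suspends |
| 3 in one SOC plus 1 in another | suspends | suspends |

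The inversion is confined to the second line: four counts, all events in one SOC. One further participant with a non-reversible event in a second SOC would trigger the row.

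**Is the count supplied elsewhere?** No. Footnote a covers injection-site reactions only. Table 20 is discretionary and has no effect in single-dose Cohorts 1 to 7. The SRC clauses in 6.6 and 9.5 provide for recommendations and a meeting, with no number attached. The remaining Table 21 rows need a different kind of event: injection site, QT, hematology, Grade III, Grade IV, serious or liver.

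**Cost of a repair.** Let p be the chance that an active participant has a non-reversible related Grade II event in the SOC concerned. The documents give no value, so p is assumed over a range. With X binomial, n = 6:

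- P(X ≥ 2) = 1 − (1 − p)^6 − 6p(1 − p)^5
- P(X ≥ 3) = P(X ≥ 2) − 15p²(1 − p)^4

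At p = 0.10: P(X ≥ 2) = 1 − 0.5314 − 0.3543 = 0.114, and P(X ≥ 3) = 0.1143 − 0.0984 = 0.016.

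| Assumed p | Literal text | ≥ 3 in one SOC | ≥ 2 in same or different SOCs |
|---|---|---|---|
| 5% | 0% | 0.2% | 3.3% |
| 10% | 0% | 1.6% | 11.4% |
| 20% | 0% | 9.9% | 34.5% |
| 30% | 0% | 25.6% | 58.0% |

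These are chances that the one-SOC pattern alone suspends a cohort. Decisions are made on blinded data (Protocol 6.6), so a placebo participant's event judged related could also count. With n = 8 and the same rate in all, the ≥ 3 and ≥ 2 figures become 3.8% and 18.7% at p = 10%, 20.3% and 49.7% at 20%, and 44.8% and 74.5% at 30%.

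**The case against.** The best answer is that the cell means a total of 2 wherever the events fall. The reversible row needs a separate one-SOC line because its one-SOC count (3) is below its across-SOC total (4). With a total of 2, a second line would be redundant or would have to be 1, so a single line is what one would expect. The QT and hematology rows also stop at 2, and footnote a ends on 2 persistent events. This is plausible and may be the intent. It is not what the words say, however: one row higher, the reference to different SOCs marks the contrast with a single SOC, and the same words are then used alone. Someone could equally carry down the count of 3 from the reversible row, which gives a different threshold.

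Other controls also narrow the exposure. Dosing is staggered 2/3/3, so on the planned schedule at most 5 participants are dosed before the last group. Every dose step except that to Cohort 5 needs SRC review, and Cohort 5 needs at least Investigator review. Grade III, Grade IV and serious events have their own triggers. All of this stands and softens the gap. But Table 21 also governs whether equal or higher dose cohorts may start, where all 6 active participants count, and discretion does not replace a numerical trigger.

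The event rates are assumptions and say nothing about actual risk; they serve only to price the repair. It is also worth confirming in the typeset table that the cell has no second line. Both lines of the neighbouring reversible cell are present in the text. The SRC charter may clarify the point, but it is not among the documents.

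**Conclusion.** The concern holds on a literal reading. For non-reversible related Grade II events confined to one SOC, 3 to 6 of 6 active participants meet no mandatory trigger, while the same number with reversible events suspends dosing. There is no inversion at 2 participants, and across different SOCs the rule is stricter for non-reversible events, as it should be. The conclusion rests on the wording of the cell as it stands. If a total of 2 in any SOC was intended, the defect is ambiguity in a mandatory safety rule, and the same edit cures it. The change should be made. Confidence is medium, because the intended meaning cannot be settled from the text.

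**What to change.** In the non-reversible Grade II row of Table 21, replace the participant count with *≥ 2 total, in the same or different SOCs*. If that is thought too sensitive, keep the existing text and add *≥ 3 in 1 SOC*, so that the row is no looser than the reversible row; the sponsor already accepts that count for reversible events. Align the SRC charter if it repeats the rule.

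The edit is one table cell, made by amendment. The price is a possible extra cohort suspension, at the rates tabulated above. If a total of 2 in any SOC is already the intended reading, the ≥ 2 option changes nothing in operation.

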5.1. Inclusion Criteria

Male and female participants are eligible to be included in the study only if all the following criteria apply:

Age

1. Participant must be 18 to 65 years of age inclusive, at the time of signing the informed consent.

Type of Participant and Disease Characteristics

2. Participants who are healthy as determined by medical evaluation with no clinically significant or relevant abnormalities as determined by medical history, physical examination, vital signs, 12-lead ECG, and clinical laboratory evaluation (hematology, biochemistry, coagulation, and urinalysis) that is reasonably likely to interfere with participation in or ability to complete the study, or to potentially confound interpretation of study results, as assessed by the Investigator and Sponsor Medical Monitor.
3. Cohort 9 only: Participants of Japanese descent (defined as those participants whose parents and grandparents are both Japanese and who have spent less than 5 years outside of Japan).

Weight

4. Body weight within 50 – 100 kg (inclusive), and body mass index (BMI) within the range 17 – 32 kg/m², (inclusive).

Sex

5. Contraceptive use by men or women should be consistent with local regulations regarding the methods of contraception for those participating in clinical studies. Female participants of childbearing potential and male participants with female partners of childbearing potential must be willing to follow protocol-specified contraception guidance while on treatment and for at least 5 months after last dose of study drug (described in Section 10.4).

Other Inclusion Criteria

6. Serum albumin above lower limit of the normal range (local laboratory) at Screening.
7. QT interval corrected using the Fridericia's formula (QTcF) \leq 450 msec at Screening and prior to dosing on Day 1.
8. Documented vaccination with MCV4 at least 56 days and not more than 2 years and 6 months prior to dosing. Documentation must include a positive titer to confirm an immune response before study drug administration.
9. Documented vaccination with serogroup B meningococcal vaccine at least 56 days and not more than 2 years and 6 months prior to dosing. For participants not previously

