8.2.3. Electrocardiograms

Triplicate 12-lead ECGs will be recorded at the time points described in the SoA (Section 1.3) to obtain heart rate, PR, QRS, and QT intervals. 12-lead ECG recordings will be made after the participants have been resting in a supine position for at least 10 minutes.

At each time point at which triplicate ECGs are required, 3 individual ECG tracings should be obtained as closely as possible in succession but no more than 2 minutes apart.

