8.2.3.1. Safety Review of 12-lead Electrocardiograms

All recorded ECGs will be reviewed by the Investigator or qualified designee. If a participant shows an abnormal ECG, additional safety recordings (including the use of 5- or 12-lead Holter equipment) may be made, and the abnormality will be followed to resolution.

8.2.3.2. 24-hour Holter Electrocardiograms/Real Time Display (Cardiac Telemetry)

Holter recording will be performed up to 3 months prior to Day 1, and telemetry will be used on dosing days as specified in Section 1.3. Electrocardiogram telemetry will be monitored by the Investigator or qualified member of clinical staff. This will allow the extraction of 10-second 12-lead ECG data files, which can be transferred onto the MUSE. All ECG files so acquired will then be analyzed and over-read using the same process as for any other 12-lead ECG. The ECG Holter/telemetry reports will be archived with study documents.

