10.3.1. Definition of AE

AE Definition

 An AE is any untoward medical occurrence in a participant, temporally associated with the use of study intervention, whether or not considered related to the study intervention. Note: An AE can therefore be any unfavorable and unintended sign (including an abnormal laboratory finding), symptom, or disease (new or exacerbated) temporally associated with the use of study intervention.

Events Meeting the AE Definition

 Any abnormal laboratory test results (hematology, clinical chemistry, or urinalysis) or other safety assessments (eg, ECG, radiological scans, vital signs measurements), including those that worsen from baseline, considered clinically significant in the medical and scientific judgment of the Investigator Exacerbation of a chronic or intermittent pre-existing condition including either an increase in frequency and/or intensity of the condition. New conditions detected or diagnosed after study intervention administration even though it may have been present before the start of the study. Signs, symptoms, or the clinical sequelae of a suspected drug-drug interaction. Signs, symptoms, or the clinical sequelae of a suspected overdose of either study intervention or a concomitant medication. Overdose per se will not be reported as an AE/SAE unless it is an intentional overdose taken with possible suicidal/self-harming intent. Such overdoses should be reported regardless of sequelae.

Events Not Meeting the AE Definition

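### The QT row of the stopping rules (Protocol Tables 20 and 21) limits uncorrected QT only; above 60 bpm a QTcF over 500 msec can sit below that limit, so a QTcF trigger should be added

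*Protocol*

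**What the plan says.** Protocol section 7.2.1, Table 20, discontinues study drug in an individual for "A prolongation of the uncorrected QT interval of greater than 500 ms, using consistent, technically valid triplicate ECG". Footnote a confines the Table 20 actions to multiple-dose regimens. Section 7.2.2, Table 21, uses the same limit, "A prolongation of the uncorrected QT interval of greater than 500 msec, using consistent, technically valid triplicate ECG". There, two or more participants suspend the rest of the cohort and all equal or higher doses. In both tables the column heading restricts every row to adverse events related to ALXN1820.

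Both tables exempt QT prolongation from the Grade II row and send it to its own row. The Grade III, Grade IV and serious rows carry no such exemption and print no QT or QTc value.

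Elsewhere the plan works with QTcF. Inclusion criterion 7 (section 5.1) requires QTcF of at most 450 msec at Screening and before dosing on Day 1. The outlier analyses in Protocol section 9.4.2.1 and SAP section 11.4 count both QT and QTcF above 500 msec. Triplicate ECGs are recorded "to obtain heart rate, PR, QRS, and QT intervals" (section 8.2.3), so QTcF can be calculated from each one.

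**The concern.** Uncorrected QT shortens as heart rate rises, so a fixed limit on QT is a different limit on QTcF at every heart rate. Above 60 bpm the printed limit is the more lenient of the two. The final tables could then list participants with QTcF above 500 msec who had not reached the QT row's limit while dosing was under way.

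This row holds the only QT number printed in the stopping rules. In the multiple-dose cohorts it bears on whether an individual receives the next dose. In every cohort it bears on whether dosing at that level and above continues, in a first-in-human study.

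**Working it through.** The plan gives a fixed cut-off with no derivation, so there is no figure of its own to reproduce.

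**Inputs.** From the Protocol: the limit of 500 msec on uncorrected QT (Tables 20 and 21), the entry limit of QTcF 450 msec (section 5.1), and the scheduled ECGs (section 1.3). The documents give no heart-rate (HR) distribution.

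**Conversion (no assumption needed).** Fridericia with RR = 60/HR seconds gives QTcF = QT × (HR/60)^(1/3), and so QT = QTcF × (60/HR)^(1/3).

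| HR (bpm) | QTcF when QT = 500 | QT when QTcF = 500 |
|---|---|---|
| 50 | 470.5 | 531.3 |
| 55 | 485.7 | 514.7 |
| 60 | 500.0 | 500.0 |
| 65 | 513.5 | 486.8 |
| 70 | 526.4 | 475.0 |
| 75 | 538.6 | 464.2 |

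Example: QT 480 at 75 bpm gives 480 × (75/60)^(1/3) = 517.1, which is over 500 on QTcF but below the row's limit.

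A given QTcF value c escapes the limit on one ECG when HR exceeds 60 × (c/500)³. That is 63.7 bpm for c = 510, 67.5 for 520 and 71.5 for 530. Below 60 bpm the direction reverses, and the row's limit is passed with QTcF still under 500.

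**Frequency (illustration only; the heart rates are assumed).** Hold QTcF at 510. Take participant mean heart rates as normal with SD 8 between participants, and within-participant SD 5. The chance that all k ECGs stay below the limit is the average over participant means M of [1 − Φ((63.7 − M)/5)]^k.

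| ECGs counted | Mean 62 bpm | Mean 70 bpm |
|---|---|---|
| 1 (brief effect) | 43% | 75% |
| 9 (single-dose cohorts, to Day 5) | 14% | 45% |
| 16 (single-dose cohorts, all visits) | 11% | 38% |

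With means of 58 to 70 bpm, between-participant SD 6 to 9 and within-participant SD 3 to 7, the nine-ECG figure runs from 1% to 62%.

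Table 20 acts only in multiple-dose cohorts, which have more ECGs. Cohorts 8 and 9 have 9 after the first dose, 4 around each of the next three doses, and a pre-dose set on Day 29: 9 + 12 + 1 = 22. At mean 62 bpm that gives 9%.

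For Table 21, with p = 0.143 (nine ECGs, mean 62 bpm) and exactly two affected participants, the limit is not reached twice with probability 1 − (1 − p)² = 27%. With three affected it is p³ + 3p²(1 − p) = 5.6%. Exactly two is the worst case for a rule that needs two.

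All these figures suppose that a QTcF of 510 occurs, and that every ECG over the limit is called a related adverse event.

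**The case against.** The strongest reply is that the QT row is no more automatic than the others. Because both tables cover only related adverse events, an ECG finding must first be "considered clinically significant in the medical and scientific judgment of the Investigator" (section 10.3.1) and then be attributed to study drug. That holds for the present row and would hold for an added QTcF limit. This stands, and it rules out contrasting an automatic QT row with judgement-based backstops.

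Second, Grade III and above do not exempt QT. One related Grade III event discontinues an individual. Two suspend all dosing, which is stricter than the QT row. Section 10.3.3 takes intensity from CTCAE v5.0, whose QT criteria are not in the documents. If those criteria include a corrected-QT cut-off, these rows may already catch the cases in question. The protocol's own gloss on Grade 3 is functional (unable to carry on normal activities), and a symptomless ECG finding does not plainly meet it, but that is one reading. The point is open either way.

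Third, there are other layers: "All recorded ECGs will be reviewed by the Investigator or qualified designee" (section 8.2.3.1), telemetry around each dose in the multiple-dose cohorts, Investigator discretion to discontinue, SRC review before most escalations, and an ad hoc SRC meeting within 24 hours of a significant safety issue. None states a QTcF cut-off, but all are real protections. The monkey studies identified no potential risks (section 2.3.1).

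What the reply does not touch is the printed limit. The documents give no reason for confining it to uncorrected QT.

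**Conclusion.** The point holds for the QT row. Its numeric limit is on uncorrected QT alone, and above 60 bpm a related event with QTcF over 500 msec can fall below it. The shortfall is exact at any given heart rate: 13.5 msec at 65 bpm, 26 at 70 and 39 at 75.

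A reader might go further and infer that the stopping rules as a whole would let such events through. The documents do not support that, because CTCAE grading under the higher-grade rows cannot be checked here, and the same judgement steps govern every row. Nor should any of the percentages be read as an expected miss rate. The heart rates are assumed, the range of 1% to 62% settles nothing, and the plan offers no distribution to narrow it.

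This is a cheap improvement to the drafting of a safety rule. No planned estimate or analysis changes, and the outlier tables already count QTcF above 500 msec.

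**What to change.** In the QT row of Tables 20 and 21, trigger on confirmed triplicate-mean QTcF above 500 msec or uncorrected QT above 500 msec. Keep the uncorrected limb: a row based on QTcF alone would act later below 60 bpm (at QT 514.7 for 55 bpm and 531.3 for 50). With both limbs no existing trigger is lost, and above 60 bpm the effective QT limit drops to the last column of the conversion table. The change leaves the adverse-event and relatedness judgement in place, and it does not remove triggers below 60 bpm where QTcF is under 500.

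The cost is the wording of one row in two tables. No new data are needed, since heart rate and QT come from every triplicate and QTcF is already required for entry and for the outlier analysis. The downside is a rare additional stop. In a simulation with no drug effect (assumed QTcF mean 405 msec, between-participant SD 16, within-participant SD 8, entry at 450 or below, 16 ECGs each), the added limb never fired in about 400,000 participants.
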